8.3 Statistical analysis of other efficacy variables

8.3.1 Derivation of other efficacy variables

8.3.1.1 Time to ACR20, ACR50, ACR70 response from Baseline

Time to a given response will be defined as the length in days from Baseline until the first date when the response is achieved.

Time from Baseline to censoring will be considered for the following subjects:

- Subjects who discontinue study treatment prior to achieving a response will be censored at the date of study treatment discontinuation.
- Subjects in the placebo group who fail to achieve a response prior to Week 16 visit will be censored at the date of the Week 16 visit.
- Subjects who reach the end of treatment without achieving the given response will be censored at the date of the end of treatment visit (for the Week 24 analysis, subjects who reached Week 24 without achieving the given response will be censored at that visit).

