2.3.2.3 Active Treatment-Blind Period

After the 16-week DBP, subjects will enter the 36-week ATP. At Week 16 (Visit 10), subjects will be allocated to treatment regimens as follows:

- Subjects in the BKZ 160mg sc Q4W group will continue to receive BKZ 160mg sc Q4W
- Subjects in the placebo group will be reallocated to BKZ 160mg sc Q4W Subjects in the ADA 40mg sc Q2W group will continue to receive ADA 40mg sc Q2W.

As for the DBP, BKZ and ADA will be administered sc by unblinded study personnel at the clinical site. The first dose in the ATP will be administered at Week 16 after all assessments have been completed.

During the 36 weeks of the ATP, IMP administration will be performed every 2 weeks (allowed visit window between 11 and 17 days) at Study visits (from Visit 10 – Week 16 through Visit 27 - Week 50).

Visit 28 (Week 52) ends the ATP, and the last assessments for that period are collected during that visit.

Subjects who withdraw early from the study will undergo the ET visit assessments and will enter the SFU Period, as applicable. Subjects who withdraw from IMP during the ATP will be encouraged to return for all remaining scheduled visits up to Week 52 and the SFU visit (20 weeks after their final dose of IMP).

At the completion of the ATP, investigators should discuss treatment options with the subject. Subjects who complete PA0010 (ie who performed all visits up to Week 52 and not having permanently discontinued IMP and who did not meet any of the withdrawal criteria) will be given the opportunity to enter the OLE study at Week 52.

The ATP starts on the day of dose administration at Week 16 and ends at Week 52 (Visit 28) or at the Early Termination visit (ET Visit) for subjects withdrawn from the study after Week 16 and before Week 52. This period should last 36 weeks maximum.

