No formal alterations to the further study conduct (eg, stopping rules, sample size re-estimation, or changes to eligibility criteria) are planned for the 2 interim analyses.

No separate SAP for the interim analyses will be provided. The TFL shells for the interim and the final analyses will be provided in the same document and appropriately identified.

The below table summarize the type of efficacy and safety analyses to be performed for the 2 interim analyses.

Table 4-4: Type of efficacy and safety tables provided for the interim analyses

Variable Type of tables	Period or Timepoint (Analysis set)	Treatment groups	Provided for Interim Analysis 1 (Week 24 analysis)	Provided for Interim Analysis 2 (Week 52 analysis)
Tables of primary efficacy variable	Week 16 (RS FAS PPS)	
 • Placebo • BKZ 160mg Q4W • ADA 40mg Q2W 	Yes	Yes, rerun of tables provided for interim analysis 1
Tables of secondary efficacy variables.	Week 4 and 16 (RS*)	
 • Placebo • BKZ 160mg Q4W • ADA 40mg Q2W 	Yes	Yes, rerun of tables provided for interim analysis 1
Tables / Graphs of time to ACR response	DBP (RS)	
 • Placebo • BKZ 160mg Q4W • ADA 40mg Q2W 	Yes, subjects not achieving response at Week 16 are censored at Week 16.	Yes, rerun of tables provided for interim analysis 1
	Overall Study Period (RS)	
 • Placebo/BKZ 160 mg Q4W • BKZ 160mg Q4W • ADA 40mg Q2W 	Yes, subjects not achieving response at Week 24 are censored at Week 24.	Yes, subjects not achieving response at Week 52 are censored at Week 52.
By-visit tables of other efficacy endpoints	Overall Study Period (RS*)	
 • Placebo / BKZ 160 mg Q4W • BKZ 160mg Q4W • ADA 40mg Q2W 	Yes, from Baseline to Week 24	Yes, from Week 0 until Week 52.
Extra by-visit tables for ACR50 and PASI90 using Baseline Week 16	ATP (ATS)	
 • Placebo / BKZ 160mg Q4W 	Yes, from Week 20 until Week 24	Yes, from Week 16 until Week 52.
Extent of exposure and time at risk	DBP (SS)	
 • Placebo • BKZ 160mg Q4W • ADA 40mg Q2W 	Yes	Yes
	ATP (ATS)	
 • Placebo / BKZ 160mg Q4W • BKZ 160mg Q4W • BKZ 160mg Q4W Total • ADA 40mg Q2W 	Yes, until Week 24	Yes

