8.3.2.1 Time to ACR20/50/70 response

The time to ACR20/50/70 response will be successively analyzed:

- For the DBP, on the 3 treatment groups (for the Week 24 analysis).
- For the overall study period, on the 3 treatment groups (for the Week 52 analysis) They will be estimated and presented using the Kaplan Meier (KM) product limit method for each of treatment groups.

The KM plots of time to ACR20,50,70 response will be presented by treatment group. The line will start at 0 and will increase over time, representing time to achieving the response (reversed KM estimates).

The median time to response, including the 2 sided 95% CI, will be calculated for each treatment group.

For the analysis on the DBP, the hazard ratio of BKZ vs. placebo as well as the corresponding 95% CI and p-value will be displayed (using SAS® PROC PHREG stratified by region and bone erosion at Baseline)

Comparisons of BKZ vs. placebo will be analyzed based on a log-rank test stratified by region and bone erosion at Baseline (0, ≥ 1) (considering that the same stratification factors have been retained for the primary efficacy analysis). This comparison will be performed using SAS® PROC LIFETEST on subjects from both treatment groups.

The time to ACR20/50/70 endpoints will be analyzed using OC data.

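### SAP 8.3.1.1 censors placebo subjects whose first ACR response is at the Week 16 visit, contradicting Table 4-4; programmed literally, it biases the double-blind hazard ratio in favour of BKZ

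*SAP*

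**What the plan says.** SAP 8.3.1.1 defines the event identically for all arms: "Time to a given response will be defined as the length in days from Baseline until the first date when the response is achieved". It then lists who is censored. One bullet applies to placebo only: "Subjects in the placebo group who fail to achieve a response prior to Week 16 visit will be censored", with the Week 16 visit date as the censoring date. The bullet is not limited to the double-blind period (DBP). For subjects in general the rule is "Subjects who reach the end of treatment without achieving the given response will be censored at the date of the end of treatment visit", with Week 24 as the cut-off in the Week 24 analysis. A third bullet censors at treatment discontinuation.

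Table 4-4 in SAP 4.3.1 gives other rules. Its DBP row covers Placebo, BKZ and ADA together: "subjects not achieving response at Week 16 are censored at Week 16". Its overall-period row includes the Placebo/BKZ group. For interim analysis 1 it censors non-responders at Week 24, and for interim analysis 2 it reads "subjects not achieving response at Week 52 are censored at Week 52".

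On timing, SAP 2.3.2.2 places the Week 16 assessments at the end of the DBP, and SAP 2.3.2.3 adds: "The first dose in the ATP will be administered at Week 16 after all assessments have been completed". SAP 8.3.1.2 lists ACR assessments at Weeks 2, 4, 8, 12 and 16 in this period. For the DBP, SAP 8.3.2.1 requires that "the hazard ratio of BKZ vs. placebo as well as the corresponding 95% CI and p-value will be displayed". It also plans a stratified log-rank test and Kaplan-Meier curves.

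**The concern.** A response seen at the Week 16 visit in a placebo subject is a response on placebo, because no BKZ has yet been given. The words *prior to* in the placebo bullet exclude it: the subject has not responded before that visit, so is censored on the very day of response. No such bullet exists for BKZ or ADA. One of the five scheduled post-Baseline ACR visits in the DBP would then yield events in the active arms but not in the placebo arm.

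This would affect the DBP hazard ratio, its confidence interval, the log-rank p-value and the placebo Kaplan-Meier curve at Week 16. The same subject could be an ACR50 responder in the primary analysis and a censored non-event here. Separately, two programmers working from 8.3.1.1 and from Table 4-4 would follow placebo subjects for different lengths of time in the overall-period analysis.

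**Working it through.** **Step 1. The two places side by side.**

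| Case | SAP 8.3.1.1 read literally | Table 4-4 |
|---|---|---|
| Placebo, first response at Week 16, DBP | censored at Week 16 | event |
| BKZ or ADA, first response at Week 16, DBP | event | event |
| Placebo/BKZ, no response by Week 16, overall period | censored at Week 16 | followed to Week 24 (interim 1) or Week 52 (interim 2) |

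The first and third rows conflict.

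**Step 2. Inputs.** From SAP 2.4.1: 420 BKZ and 280 placebo subjects, with ACR50 rates of 43.8% and 16%. The SAP's own figures reproduce: the difference is 43.8 − 16 = 27.8 points, the odds ratio is (0.438/0.562)/(0.16/0.84) = 4.09, and power is above 99.99% with or without continuity correction, against the stated >99%. The SAP gives no hazard ratio, event count or distribution of first-response times for this endpoint. The design rates serve here only as anchors.

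**Step 3. Direction and approximate size.** The literal rule censors on the response date itself, so placebo time at risk is unchanged and only the placebo event count falls, by the share f that first respond at Week 16. The placebo event rate is multiplied by (1−f), so the BKZ/placebo hazard ratio is multiplied by about 1/(1−f). Expected placebo events are 280 × 0.16 = 44.8. The rule would discard about 4.5 of them at f = 10% and about 17.9 at f = 40%. Without dropout, the placebo curve at Week 16 would show 16% × (1−f), that is 14.4% or 9.6% instead of 16%.

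**Step 4. Cox model check.** First-response times were placed at Weeks 2, 4, 8, 12 and 16. Assumptions: 16% and 43.8% are cumulative first-response rates by Week 16; f is the same in both arms; no dropout; unstratified model with Breslow ties.

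| Assumed f | HR, Table 4-4 rule | HR, literal 8.3.1.1 | Ratio | 1/(1−f) |
|---|---|---|---|---|
| 10% | 3.12 | 3.45 | 1.11 | 1.11 |
| 20% | 3.13 | 3.89 | 1.24 | 1.25 |
| 30% | 3.12 | 4.42 | 1.42 | 1.43 |
| 40% | 3.09 | 5.12 | 1.66 | 1.67 |

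The inflation follows the placebo share. With f = 30% on placebo but 15% on BKZ, the hazard ratio goes from 3.19 to 4.50, a factor of 1.41.

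**Step 5. A reference point for f.** Under a constant placebo hazard reaching 16% at Week 16, the cumulative rate at Week 12 is 1 − 0.84^0.75 = 12.3%. Then f = (16 − 12.3)/16 ≈ 23% and the factor is about 1.3.

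**Step 6. No treatment effect.** With a 16% rate in both arms, 2,000 simulated trials per setting and visits varying by ±2 days, the two-sided 5% unstratified log-rank test rejected in 8.5%, 19% and 38% of trials at f = 10%, 20% and 30% under the literal rule. Under Table 4-4 the figures were 5.6%, 4.4% and 4.9%.

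**The case against.** The strongest reply is that the bias is conditional. SAP 8.3.1.1 contains no DBP cut-off for BKZ or ADA, so stopping those arms at Week 16 has to come from Table 4-4. A programmer who takes the DBP row of that table for all three arms gets a symmetric analysis with no bias. The event definition at the head of 8.3.1.1 also fits a Week 16 placebo response, and *prior to* may be loose drafting for *by*.

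That much stands, and it limits the conclusion. A reader might infer that the DBP hazard ratio is certain to be biased. The document does not support that, because it contains two rules and only one of them distorts the result. The reply does not remove the contradiction. 8.3.1.1 is the derivation section, its placebo bullet is explicit, and the overall-period conflict remains even if *prior to* is read as *by*.

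A reader might also infer that the hazard ratio would rise above 5. That needs about 40% of placebo first responses to fall at Week 16. The SAP gives no such share, and a constant hazard suggests a smaller one.

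Finally, a reader might infer a threat to the trial's main claim. There is none: time to ACR response is listed among the other efficacy variables (SAP 2.2.1.3), is not one of H1–H9 in Table 4-5, and does not enter the Week 16 logistic regression of SAP 8.1.2.

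**Conclusion.** The contradiction is certain on the text, both for the DBP and for the overall period. The direction of the DBP bias is also certain if 8.3.1.1 is followed literally, because events are removed from the placebo arm alone. The size is not known. It rests on an assumed f of 10–40%, which gives an inflation of about 1.1–1.7, and on design rates treated as cumulative first-response rates without dropout. ACR20 and ACR70 fall under the same rule, but the figures here use the ACR50 design rates only.

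The overall-period conflict affects the Kaplan-Meier curves and medians, and any log-rank test run on that period. SAP 8.3.2.1 specifies a hazard ratio for the DBP only. The point should be corrected, but no confirmatory result depends on it.

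**What to change.** For the DBP analysis, state in 8.3.1.1 that subjects in every arm without a response up to and including the Week 16 visit are censored at that visit, and that a response at Week 16 is an event. Retain the discontinuation rule.

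For the overall-period analysis, either make placebo censoring in 8.3.1.1 agree with Table 4-4 (Week 24 for interim analysis 1, Week 52 for interim analysis 2), or state in both places that the placebo curve stops at Week 16.

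The cost is a few lines of SAP wording and one line of derivation code. No additional data are needed.

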8.3.1.2 ACR20, ACR50 and ACR70

Method for derivation of ACR50 can be found in [Section 8.1.1](#). ACR20 and ACR70 will be derived similarly except that they will be based on a 20% and on 70% improvement from Baseline.

ACR20, ACR50 and ACR70 responses will be analyzed at Week 2, 4, 8, 12, 16, 20, 24, 28, 32, 36, 44, 52.

For the placebo group, ACR50 response will be presented both based on the Day 1 Baseline and on the Week 16 Baseline (on the ATS, for the ATP, for subjects switching to BKZ at Week 16).

8.3.1.3 PASI75, PASI90 and PASI100 response (in subjects with PSO involving at least 3% of BSA at Baseline)

Method for derivation of PASI score can be found in [Section 8.2.1.2](#).

PASI75, PASI90, PASI100 are binary variables equal to 1 if the percentage improvement from Baseline in the PASI scores is $\geq 75\%$, $\geq 90\%$, 100% and 0 if the percentage improvement from Baseline is $< 75\%$, 90%, 100%.

PASI75, PASI90, PASI100 as well as the PASI score and the change from Baseline for subjects with PSO involving at least 3% of BSA at Baseline will be analyzed at Week 2, 4, 8, 12, 16, 20, 24, 28, 32, 36, 52.

For the placebo group, PASI90 responses will be determined both based on the Day 0 Baseline and on Week 16 Baseline (on the ATS, for the ATP, for subjects switching to BKZ at Week 16).

8.3.1.4 Composite endpoints composed of ACR50 and PASI90 and ACR50 and PASI100 responses (subjects with PSO involving at least 3% of BSA at Baseline)

The composite endpoint composed of ACR50 and PASI90 is a binary variable equal to 1 for subjects responding to ACR50 (ACR50=1) and PASI90 (PASI90=1).

The composite endpoint will be equal to 0 if ACR50=0 or PASI90=0 regardless of whether any of the 2 endpoints is missing.

The same rules as above will be applicable for the composite endpoint on ACR50 and PASI100.

The composite endpoints will be missing if both endpoints are missing or if any of the 2 is missing and the other one equal to 1.

Each endpoint (ACR50 and PASI90 or PASI100) will be imputed separately before deriving the composite endpoint.

The composite endpoints for subjects with PSO involving at least 3% BSA at Baseline will be analyzed at Week 2, 4, 8, 12, 16, 20, 24, 28, 32, 36, 52.

8.3.1.5 Proportion of Psoriatic Arthritis Response Criteria (PsARC) responders

The PsARC is based on the TJC (68 joints) and SJC (66 joints), the PGA-PsA and PhGA-PsA. The PsARC response is defined as improvement from Baseline in at least 2 of the 4 measures (TJC, SJC, PGA-PsA, PhGA-PsA) 1 of which must be TJC or SJC and no worsening from Baseline in any of the 4 measures:

- Improvement for TJC and SJC is defined as a reduction of $\geq 30\%$. Improvement for PGA-PsA and PhGA-PsA is defined as a reduction of the 100-point VAS of ≥ 20 points
- Worsening for TJC and SJC is defined as an increase of $\geq 30\%$. Worsening for PGA-PsA and PhGA-PsA is defined as an increase of the 100-point VAS of ≥ 20 .

PsARC response will be analyzed at Week 2, 4, 8, 12, 16, 20, 24, 36, 52.

8.3.1.6 Psoriatic Arthritis Disease Activity Score (PASDAS) categories and change from baseline in PASDAS

The PASDAS is a composite score that includes patient and physician global scores of skin and joint disease, SJC, TJC, LEI, tender dactylitis count (sum of tenderness scores), the physical component of the SF-36 Health Survey, and level of hs-CRP. PASDAS is calculated using the following equation:

$$\begin{aligned} \text{PASDAS} = & \left((0.18 \times \sqrt{\text{Physician global VAS}}) + (0.159 \times \sqrt{\text{Patient global VAS}}) \right. \\ & - (0.253 \times \sqrt{\text{SF36 PCS}}) + (0.101 \times \text{LN}(\text{SJC} + 1)) + (0.048 \times \text{LN}(\text{TJC} + 1)) \\ & + (0.23 \times \text{LN}(\text{LEI} + 1)) + (0.377 \times \text{LN}(\text{Tender dactylitis count} + 1)) \\ & \left. + (0.102 \times \text{LN}(\text{hs-CRP} + 1) + 2) \right) * 1.5 \end{aligned}$$

Note: LN=natural logarithm

If Tender Dactylitis count is missing because LDI=0 at Baseline, Tender Dactylitis count will be replaced by 0 in the formula.

If for any other reason a PASDAS component is missing, PASDAS will be set to missing.

The following categories are used to define the level of disease activity:

- Remission: PASDAS ≤ 1.9
- Low disease activity: PASDAS > 1.9 to < 3.2
- Moderate disease activity: PASDAS 3.2 to < 5.4
- High disease activity: PASDAS ≥ 5.4

The PASDAS categories and the change from Baseline in PASDAS score will be analyzed at Week 4, 16, 24, 36, 52.

8.3.1.7 ACR50 responders at Week 16 and maintaining response at post-Week 16 visits up to Week 52

For subjects who have an observed ACR50 response at Week 16, the ACR50 responders at Week 52 will be presented.

This summary will be presented on the ATS by randomized treatment for responder subjects at Week 16.

ACR50 responses for subjects responding at Week 16 will be analyzed at Week 20, 24, 28, 32, 36, 44, 52.

8.3.1.8 MDA response

Method for derivation of the MDA response can be found in [Section 8.2.1.4](#).

MDA response will be analyzed at Week 4, 8, 12, 16, 20, 24, 36, 52.

8.3.1.9 Very Low disease activity (VLDA) response

Like MDA, VLDA is a state of disease activity deemed a useful target of treatment by both the subject and physician, given current treatment possibilities and limitations.

A subject is considered as having VLDA if all 7 of the criteria used for MDA and listed in [Section 8.2.1.4](#) are fulfilled.

If any of the 7 MDA criteria is not met, then the subject will be considered as non-responder.

VLDA response will be analyzed at Week 4, 8, 12, 16, 20, 24, 36, 52.

8.3.1.10 Proportion of Subjects with an IGA score of 0 (clear) or 1 (almost clear) AND at least a 2-grade reduction from Baseline in the subset of subjects with psoriatic skin lesions at Baseline

Method for derivation of this variable can be found in [Section 8.2.1.10](#).

The proportion of subjects with an IGA score of 0 (clear) or 1 (almost clear) AND at least a 2-grade reduction from Baseline in the subset of subjects with psoriatic skin lesions at Baseline will be analyzed at Week 4, 8, 12, 16, 20, 24, 36, 52.

For some subjects with BSA $\geq 3\%$ at Baseline, IGA data have not been captured at some post-Baseline visits when BSA $< 3\%$ at those visits. To address that, an additional supportive analysis will be performed in which these subjects will be considered as IGA responders at the respective visit.

In the context of this analysis, observed data for % of BSA affected by PSO will be also analyzed by visit using descriptive statistics.

8.3.1.11 Disease Activity Index for Psoriatic Arthritis (DAPSA) score, state and change from Baseline in DAPSA score

Disease Activity Index for Psoriatic Arthritis (DAPSA) is a composite score of patient global and pain VAS, TJC, SJC and hs-CRP (mg/L) that incorporates a pattern of peripheral arthritis that often is encountered in PsA. DAPSA score will be calculated as follows:

$$DAPSA = SJC + TJC + PGA-Arthritis + PtAAP + hs-CRP$$

where:

- SJC range from 0 to 66
- TJC ranges from 0 to 68
- PGA-Arthritis represents the patient's global assessment of arthritis ranging from 0 to 10 ; 0=best, 10=worst (using the unrounded VAS value that ranges from 0 to 100 mm and dividing this value by 10) ([Section 8.3.1.28](#))
- PtAAP ranging from 0 to 10, 0=best, 10=worst, (unrounded, by dividing the original value by 10)
- hs-CRP in mg/L (no upper limit applied).

DAPSA values will be categorized in the following disease activity states:

- Remission (REM) (DAPSA≤4)
- Low Disease Activity (LDA) (DAPSA >4 and ≤14)
- Medium Disease Activity (MDA) (DAPSA >14 and ≤28)
- High Disease Activity (HDA) (DAPSA>28).

For analyses with imputation of missing data, the imputed value for DAPSA will be based on the imputed values for the individual components.

For the OC analyses, if any individual component score is missing, the DAPSA score will be set to missing.

DAPSA state, DAPSA scores and changes in scores from Baseline will be analyzed at Week 2, 4, 8, 12, 16, 20, 24, 28, 32, 36, 44, 52.

8.3.1.12 Change from Baseline in the Disease Activity Score-28 based on C-reactive protein (DAS28[CRP])

The components for DAS28[CRP] include:

- the TJC and SJC based on 28 joints ([Section 8.1.1.1](#)):
 - Upper extremity (26) - bilateral shoulders, elbows, wrists (includes radiocarpal, and carpal and carpometacarpal bones considered as a single unit), metacarpophalangeal joints I, II, III, IV, and V, thumb interphalangeals, proximal interphalangeal II, III, IV, and V.
 - Lower extremity (2) - knees.
- the PGA-Arthritis (ranging from 0 to 10 by dividing the original value by 10)
- the hs-CRP (in mg/L).

The DAS28[CRP] is calculated as follows:

$$DAS28[CRP] = 0.56 \times \sqrt{TJC} + 0.28 \times \sqrt{SJC} + 0.014 \times \text{PGA-Arthritis} + 0.36 \times \ln(hs-CRP + 1) + 0.96$$

For analyses with imputation of missing data, the imputed value for DAS28[CRP] will be based on the imputed values for the individual components.

For OC analyses, if any individual component score is missing, the DAS28[CRP] score will be set to missing.

The changes from Baseline in DAS28[CRP] will be analyzed at Week 2, 4, 8, 12, 16, 20, 24, 28, 32, 36, 44, 52.

8.3.1.13 Change from Baseline in all individual ACR core components

Individual ACR components (as listed in [Section 8.1.1](#)) are:

- SJC
- TJC
- HAQ-DI

- PtAAP
- PhGA-PsA
- PGA-PsA
- hs-CRP.

The change from Baseline (ratio from Baseline for hs-CRP) for each of the ACR components will be summarized at Week 2, 4, 8, 12, 16, 20, 24, 28, 32, 36, 40 (for SJC, TJC and hs-CRP), 44, 48 (for hs-CRP only), 52.

8.3.1.14 Change from Baseline in vdHmTSS total score and in erosion and joint space narrowing (sub-scores)

Scoring of vdHmTSS can be found in [Section 8.2.1.5](#).

The change from Baseline in vdHmTSS total score, erosion sub-score and joint space narrowing sub-score will be analyzed at Week 16, 52, on the radiographic set (successively on the overall population, on subjects with elevated hs-CRP and/or with at least one bone erosion at Baseline and on subjects without elevated hs-CRP and without bone erosion at Baseline).

At Week 16 and 52, imaging data collected outside ± 14 days around the expected visit date will be excluded from the analysis.

8.3.1.15 Percentage of subjects with no radiographic joint damage progression (Change from Baseline vdHmTSS of ≤ 0.5)

The higher the vdHmTSS score is the more radiographic damage the Subject will have.

The absence of joint damage progression (ie, stabilization or improvement in radiographic damage from Baseline) is then considered is the change of score from Baseline is ≤ 0.5 .

The percentage of subjects with no joint damage progression will be analyzed at Week 16 and 52 on the radiographic set (successively on the overall population and on subjects with elevated hs-CRP and/or with at least one bone erosion at Baseline).

8.3.1.16 Dactylitis-free state based on the LDI and change in LDI from Baseline in the subgroup of subjects with dactylitis at Baseline

Dactylitis-free state is based on a Leeds Dactylitis Index (LDI) of 0, for subjects with dactylitis at Baseline ($LDI > 0$) ([Section 8.2.1.7](#)).

The percentage of subjects with dactylitis free-state and the change from Baseline in LDI (on the subgroup of subjects with dactylitis at Baseline) will be analyzed at Week 4, 8, 12, 16 on the pooled Sample of PA0010 and PA0011 subjects (for subjects in the BKZ 160mg Q4W and the Placebo groups) and at Week 4, 8, 12, 16, 20, 24, 36, 52 on PA0010 subjects.

8.3.1.17 Enthesitis-free state based on the LEI and change in LEI from Baseline in the subgroup of subjects with enthesitis at Baseline

Enthesitis-free state is based on a Leeds Enthesitis Index (LEI) of 0, for subjects with enthesitis at Baseline ($LEI > 0$) ([Section 8.2.1.6](#)).

The percentage of subjects with enthesitis-free state and the change from Baseline in LEI (on the subgroup of subjects with enthesitis at Baseline) will be analyzed at Week 4, 8, 12, 16 on the pooled Sample of PA0010 and PA0011 subjects (for subjects in the BKZ160mg Q4W and the Placebo groups) and at Week 4, 8, 12, 16, 20, 24, 36, 52 on PA0010 subjects.

8.3.1.18 Enthesitis-free state based on the SPARCC index and change in SPARCC from Baseline in the subgroup of subjects with enthesitis at Baseline

Enthesitis-free state is based on a SPARCC index of 0, for subjects with enthesitis at Baseline (SPARCC>0) ([Section 8.2.1.12](#)).

The percentage of subjects with enthesitis-free state and the change from Baseline in the SPARCC index (on the subgroup of subjects with enthesitis at Baseline) will be analyzed at Week 4, 8, 12, 16 on the pooled Sample of PA0010 and PA0011 subjects (for subjects in the BKZ160mg Q4W and the Placebo group) and at Week 4, 8, 12, 16, 20, 24, 36, 52 on PA0010 subjects.

8.3.1.19 Proportion of subjects with a decrease of HAQ-DI from Baseline of at least 0.35 in the subgroup of subjects with Baseline HAQ-DI \geq 0.35

The proportion of HAQ-DI responders (subjects with a decrease of HAQ-DI from Baseline of at least 0.35 for subjects with HAQ-DI \geq 0.35 at Baseline) will be analyzed at Week 2, 4, 8, 12, 16, 20, 24, 28, 32, 36, 44, 52.

In addition, subgroup analyses will be performed on the HAQ-DI response at Week 16. Refer to [Section 4.8](#) for the list of subgroups of interest. The same analysis method used for the subgroup analysis of the primary endpoint will be performed and the results will be presented similarly.

8.3.1.20 Change from Baseline in the Bath Ankylosing Spondylitis Disease Activity Index (BASDAI) in the subgroup of subjects with axial involvement defined by a score of \geq 4 at Baseline

The BASDAI measure the disease activity of ankylosing spondylitis. The BASDAI is a validated self-reported instrument which consists of 6 horizontal Numeric Rating Scales, each with 10 units to measure the severity of the 5 major symptoms: fatigue, spinal pain, peripheral joint pain and swelling, enthesitis, and morning stiffness (both severity and duration) over the last week. To give each symptom equal weighting, the average of the 2 scores relating to morning stiffness is taken. The resulting 0 to 50 sum score is divided by 5 to give a final BASDAI score between 0 and 10, with lower scores indicating lower disease activity.

The BASDAI is calculated as follows:

$$BASDAI = \frac{Q1 + Q2 + Q3 + Q4 + \left(\frac{Q5 + Q6}{2} \right)}{5}$$

where Q1 – Q6 are the 6 questions from the BASDAI questionnaire.

If 1 of the 2 morning stiffness measurements (ie, questions: “How would you describe the overall level of morning stiffness you have had from the time you wake up?” and “How long does your

morning stiffness last from the time you wake up?”) is missing, the other one will be used for the morning stiffness calculation.

If 1 major symptom of the BASDAI is missing, the total score of the remaining symptoms will be divided by the number of symptoms assessed. If more than 1 major symptom is missing, the total BASDAI score will be set to missing.

Change from Baseline in BASDAI will be analyzed for subjects with axial involvement at Baseline (BASDAI \geq 4) at Week 4, 8, 12, 16, 24, 36, 52.

8.3.1.21 Change from Baseline in the modified Nail Psoriasis Severity Index (mNAPSI) score in the subgroup of subjects with psoriatic nail disease at Baseline

Subjects with psoriatic nail disease will have a target nail selected at the Baseline visit for evaluation using the mNAPSI. The nail selected should be the most affected nail observed at Baseline and should be the only one assessed throughout the study. The target nail will be scored (0 to 3) for onycholysis/oil drop dyschromia, nail plate crumbling, and pitting and will be scored (0 for “no” or 1 for “yes”) for leukonychia, nail bed hyperkeratosis, splinter hemorrhages, and red spots in the lunula. The total score (also called the mNAPSI score) will then range from 0 to 13 with higher scores indicative of more severe nail disease.

If any of the 7 response items that contribute to mNAPSI is present, while other items are missing (ie partial mNAPSI data), then the missing items are assumed to be 0 for the mNAPSI calculation. In some cases, the data may be captured in such a way that only non-zero component scores are present in the database. Again, those components that are not present are simply assumed to be 0 for the mNAPSI calculation.

Change from Baseline in mNAPSI and mNAPSI resolution (mNAPSI=0 at post-baseline assessments) will be analyzed for subjects with psoriatic nail disease at Baseline (mNAPSI score $>$ 0) at Week 4, 8, 12, 16, 24, 36, 52.

